# 1.1 SYNOPSIS

Title:	SUPERPULSED THULIUM FIBER LASER VS. PULSE MODULATED HIGH POWER HOLMIUM: YAG LASER FOR RETROGRADE INTRARENAL SURGERY
Grant Number:	N/A
Study Description:	
 
This is a randomized prospective study comparing the stone free rate and operative efficiency of two leading contemporary laser systems used during retrograde intrarenal surgery for kidney stone disease. We will compare the following two systems:
 
1. A superpulsed thulium fiber laser (thulium)
 
2. A pulse modulated high power holmium laser (Holmium)
 

Objectives * :	Aim: To determine which laser system has superior outcomes as measured by post-operative stone-free status and intraoperative efficiency metrics
	Research Question: During retrograde intrarenal surgery for kidney stone disease, which contemporary laser system (thulium vs. holmium) has a superior stone free rate?
	Null hypothesis: During retrograde intrarenal surgery for kidney stone disease, there is no difference in stone free rates between the two laser systems.
	Alternative Hypothesis: During retrograde intrarenal surgery for kidney stone disease, the thulium laser has a superior stone free rate.
Endpoints * :	
 
Primary Endpoint:
 
Stone-free status as determined by a post-operative CT scan.
 

	
 
Secondary Endpoints:
 
The secondary endpoints to be collected will pertain to efficiency metrics as produced by the laser systems: 
 
Fragmentation speed = stone volume/lasing time (mm3/sec)
 
Energy Utilization = Laser energy/volume of stone (J/mm3)
 
Lasing Activity: Lasing time/lithotripsy operative time (%)
 
Operative time (minutes)
 
Lasing time (seconds)
 
Lithotripsy operating time (seconds)
 
Treatment time (seconds)
 
 
 

Study Population:	We anticipate a sample size of 82 subjects enrolled in this study. Adult patients 18-years of age and older with non-obstructing kidney stones undergoing planned retrograde intrarenal surgery with laser lithotripsy.
Description of Sites/Facilities Enrolling Participants:	[name] currently operates twice a week at Mount Sinai West (formerly Mount Sinai Roosevelt Hospital), located at [name]. In addition, he sees patients in the clinic at the following sites: Department of Urology Faculty Practice at [name]; Midtown Urology FPA at [name].
	Patient enrollment will occur at these clinical sites, while data collection will occur in the operating room at Mount Sinai West. Data analysis will occur at a site within the Mount Sinai Health System.
Description of Study Intervention/Experimental Manipulation:	The study intervention includes comparing two standard of care laser devices for laser lithotripsy of kidney stones. The laser device allocated to each study subject will be allocated by blinded randomization.
Study Duration * : Participant Duration:	24 months 3 months

1.2	SCHEMA	
	Screening -30 to Day 1	Pre-screen potential participants by inclusion and exclusion criteria during office consultation schedule.

Visit 1

Conduct informed consent process in pre-operative area day of surgery

Randomize (n=82)

Ho: YAG N = 41 Thulium N = 41

Visit 2 Week 8 ± 2 Weeks

Follow-up visit

Final Assessments Stone free rates evaluated by CT scans

## 1.3 SCHEDULE OF ACTIVITIES

	Screening	Visit 1 Day 1 (Surgery)	Visit 2 Week 8 ± 2	Unscheduled Visit
EMR Review Eligibility	х			
Informed Consent		х		
Demographics	х			
Clinical history	х			
Height & Weight	х			
Outcome Evaluation				
Stone Free Rate			х	
Efficiency Metrics		х		
Randomization		х		
Control & Experimental Interventions		х	Х	
Adverse Events Reporting		х	х	х

## 2 INTRODUCTION

#### 2.1 STUDY RATIONALE/BACKGROUND

Kidney stone disease is one of the most common and painful conditions encountered in urologic practice. Retrograde intrarenal surgery with laser lithotripsy is the most commonly used standard of care treatment option for kidney stones and has been utilized for several decades. Advances in laser technology have progressively improved the efficacy and efficiency of the procedure. Currently, two laser systems are widely considered to be the most efficacious for this procedure: the superpulsed thulium fiber laser system and the pulse modulated high power holmium:YAG laser system. We routinely utilize either of these laser types when performing retrograde intrarenal surgery with laser lithotripsy for renal stones. However, to date, there have been no high-quality head-to-head randomized controlled trials comparing these two laser types to one another.

The closest such study compared the superpulsed thulium fiber laser system to an antiquated holmium: YAG laser system without pulse modulation and high-power output capabilities. The former resulted in a superior stone free rate (86% vs. 49%). However, the relative efficacy of the superpulsed thulium fiber laser compared to a contemporary pulse modulated high power Holmium:YAG laser remains largely unknown. To this end, the present study is a randomized prospective study comparing the stone-free

rate and operative efficiency of these two leading contemporary laser systems used during retrograde intrarenal surgery for kidney stone disease.

# 2.2 RISK/BENEFIT ASSESSMENT

# 2.2.1 KNOWN POTENTIAL RISKS

With the exception of data-safety risk, participation in this study offers no additional risk compared to non-participation. Excluding data safety risk, the risks of participation are inherent to the standard of care procedure that the patient has consented to regardless of their participation in the study (retrograde intrarenal surgery with laser lithotripsy). These risks include bleeding, infection, damage to surrounding structures, and postoperative pain, which are inherent in all surgical procedures.

# 2.2.2 KNOWN POTENTIAL BENEFITS

There are no potential benefits to participants.

# 2.2.3 ASSESSMENT OF POTENTIAL RISKS AND BENEFITS

This study involves randomization of patients to one of two available laser systems that are used as standard of care for the treatment of kidney stones. In our practice, both laser systems are readily available and routinely used as a matter of surgeon preference and can be used interchangeably. This study poses no additional risks (outside of data-safety risk) to patients undergoing retrograde intrarenal surgery, which would have been recommended regardless of whether the patient was a study participant. Risks related to retrograde intrarenal surgery include infection, bleeding, and pain. These potential risks commonly exist with surgery but are rarely expected with this type of surgical procedure

# **3** OBJECTIVES AND ENDPOINTS

OBJECTIVES	ENDPOINTS	JUSTIFICATION FOR	PUTATIVE
		ENDPOINTS	MECHANISMS OF
			ACTION
Primary			
To determine which laser	Stone free status as	Stone free status on 2 month	N/A
system (if any) offers superior	determined by 2-	follow up CT scan is the most	
efficacy.	month postoperative	accurate evaluation for complete	
	CT scan	resolution of a patient's kidney	
		stone burden	

OBJECTIVES	ENDPOINTS	JUSTIFICATION FOR	PUTATIVE
		ENDPOINTS	MECHANISMS OF
			ACTION
Secondary			
To determine which laser system (if any) offers superior efficiency.	Fragmentation speed, lasing activity, and energy utilization	These intraoperative laser metrics allow for the evaluation of intraoperative laser efficiency	N/A

## 4 STUDY DESIGN

### 4.1 OVERALL DESIGN

This is a randomized prospective study comparing the stone free rate and operative efficiency of two leading contemporary laser systems used during retrograde intrarenal surgery for kidney stone disease.

#### 4.2 SCIENTIFIC RATIONALE FOR STUDY DESIGN

Randomization allows for elimination of potential bias. Because both laser systems are used routinely in the OR as a matter of surgeon preference, any source of bias will be prevented by using a randomized study design.

## 4.3 JUSTIFICATION FOR INTERVENTION

Both laser interventions are used as standard of care but a head-to-head comparison of the stone free rates has not been studied in a prospective randomized study. Study participation requires no additional visits or excessive effort placed upon the study participants as standard of care intervention and follow will be the same regardless of study participation or not.

#### 4.4 END-OF-STUDY DEFINITION

The study will end when all patients have been enrolled and data has been analyzed.

# **5 STUDY POPULATION**

#### 5.1 INCLUSION CRITERIA

- Undergoing single stage unilateral RIRS for total stone burden volume >5mm to < 20 mm
- Must have preop CT scan to measure HU and measurements

## 5.2 EXCLUSION CRITERIA

- Anatomic variations: horseshoe kidney, pelvic kidney, ptotic kidney, urinary diversion or ureteral stricture
- Ureteral stent
- Uric acid component >50% on stone analysis
- Prior ureteroscopy within 6 weeks of current surgery
- Irreversible coagulopathy
- Urothelial tumor(s), direct extraction of the stone(s) without needing laser lithotripsy, and failure to reach the stone in the upper urinary tract with the ureteroscope.

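### Section 5.2 excludes patients for events seen only during surgery, after randomisation, while 9.2 analyses all enrolled; state that such patients stay in the primary analysis and give one outcome rule.

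*Combined protocol and SAP*

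**What the plan says.** The last bullet of section 5.2 joins three items: urothelial tumour, and then "direct extraction of the stone(s) without needing laser lithotripsy, and failure to reach the stone in the upper urinary tract with the ureteroscope". The last two can be known only during the operation. A tumour may be known beforehand or may be found only at ureteroscopy.

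Randomisation comes first. Section 6.1.1 places it before surgery, the schema (1.2) and schedule (1.3) place it at Visit 1 on the day of surgery, and section 6.3 has the allocation drawn before the study starts. Section 7.2 counts a patient as enrolled from signed consent, and section 9.2 puts every enrolled patient into the analyses. That is the only analysis-population rule in the document.

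The primary endpoint is "Stone-free status as determined by a post-operative CT scan" (1.1), timed at 2 months in section 3. Section 6.3 says that operators cannot be blinded, and section 6.1.1 allows the attending surgeon slight variations in technique.

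**The concern.** For a randomised patient whose stone is lifted out whole or cannot be reached, 5.2 says exclude and 9.2 says include. A criterion that can be met only during the operation can act only by removing someone already randomised.

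Whether to extract a stone directly or to laser it is partly the surgeon's judgement, made knowing the assigned laser. Dropping patients on that judgement is selection after randomisation on something related to the primary endpoint, because a stone extracted whole is likely to leave the patient stone-free.

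There is also a gap that 9.2 does not fill. The plan does not say how to score a patient whose stone was not reached and who has no CT, or who is treated again before the CT. If both matters stay open, the choice could be made after results by arm are known.

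**Working it through.** **1. The passages side by side**

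| Step | Section | Content |
|---|---|---|
| Consent, which is enrolment | 7.2 | before surgery |
| Randomisation | 6.1.1, 1.2, 1.3 | before surgery, Visit 1 |
| Direct extraction or failed access | 5.2 | known only during surgery; listed as exclusions |
| Analysis set | 9.2 | all enrolled |

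No passage ranks 5.2 against 9.2.

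**2. The plan's sample size (9.1)**

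Inputs: 66% vs 33%, 80% power, 5% alpha (taken as two-sided). Unpooled formula: (1.960 + 0.842)² × (0.66×0.34 + 0.33×0.67) / 0.33² = 32.1, so 33 per arm and 66 in total, as stated. Allowing for 20% dropout, 66/0.8 = 82.5, against 82 stated. The plan's figure reproduces. Section 9.1 ties the allowance to failure to follow up and does not mention intraoperative exclusions.

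**3. Bias if 5.2 is applied**

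Suppose there is no laser effect, a stone-free rate p in both arms, and a share e of an arm removed whose own stone-free rate is h. The remaining rate is (p − e·h)/(1 − e). If e and h are equal in the two arms, the difference stays zero. The documents give neither e nor h.

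On assumed values only (p = 60%, h = 95%), the remaining rate is 58.2% for e = 5%, 56.1% for e = 10% and 51.3% for e = 20%. Removing 10% from one arm and 5% from the other gives a spurious difference of about 2 points; 20% and 5% gives about 7. These show how the bias would arise and do not estimate it.

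**4. Power: keeping against excluding**

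Pooled test, which a Kruskal-Wallis test on a binary outcome (9.3.2) essentially is:

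power = Φ{[|p1 − p2| − 1.96·√(2·p̄(1 − p̄)/n)] / √([p1(1 − p1) + p2(1 − p2)]/n)}

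With d lost, n = 41(1 − d) per arm: 32.8 at the 20% of section 9.1, and 38.95 at an assumed 5% (7.3 expects very little loss). Let e be the share not lasered, assumed equal in both arms. Excluding them gives n(1 − e) per arm at 66% vs 33%. Keeping them, with a common outcome rate (tried at 0, 50% and 95%), gives n per arm and a difference of (1 − e) × 33 points: 31.4 at e = 5%, 29.7 at e = 10%.

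| Lost | Not lasered | Power, excluded | Power, kept | Cost of keeping (points) |
|---|---|---|---|---|
| 20% | 0 | 77.5% | 77.5% | 0 |
| 20% | 5% | 75.3% | 72.9–73.1% | 2.2–2.4 |
| 20% | 10% | 72.9% | 68.0–68.5% | 4.4–4.9 |
| 5% | 0 | 84.4% | 84.4% | 0 |
| 5% | 5% | 82.4% | 80.2–80.4% | 2.0–2.2 |
| 5% | 10% | 80.3% | 75.6–76.1% | 4.2–4.7 |

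The 77.5% with nobody excluded reflects the gap between the pooled test and the unpooled formula behind the 33 per arm. It does not come from 5.2. On the unpooled formula at 20% lost, the base is 80.8%; excluding 5% or 10% gives 78.8% or 76.6%, and keeping them with a common outcome of all failures gives 76.4% or 71.8%. The levels are higher and the cost of keeping is the same size.

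**5. Weight of one patient**

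Rescoring one patient moves an arm's rate by 1/41 = 2.4 points if all 41 are analysed, or 1/33 = 3.0 points if about 33 are.

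**The case against.** The best reply is that 5.2 is an eligibility list and 9.2 is the analysis rule, so the plan already keeps these patients and no bias arises. As a plain reading of 9.2 this stands. It does not settle the matter, because 5.2 is equally current, these criteria have no use before randomisation, and 9.2 gives no outcome rule.

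A reader might go further and infer that the trial will exclude these patients, or that the comparison is biased by some stated amount such as the 7 points above. The documents support neither. The 7 points need an assumed fourfold imbalance and an assumed 95% rate. Section 2.2.3 describes the lasers as "routinely used as a matter of surgeon preference and can be used interchangeably", one surgeon performs the procedures (6.2.1), and nothing links failed access to the laser. These passages weigh against a large difference between arms but do not remove the risk, since that surgeon is unblinded.

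It is also true that power does not argue for the fix: keeping these patients costs more power than excluding them. And a prespecified lasered-only primary set would remove the contradiction too, but would leave the primary result exposed to selection after randomisation.

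**Conclusion.** The point holds as a conflict between two current rules, together with a missing outcome rule. It must be resolved because it decides who enters the primary analysis, and it cannot be resolved credibly once results by arm are known.

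The harm is conditional. It arises only if 5.2 is applied after randomisation and the removed patients differ between arms in number or outcome. Its size cannot be derived from the documents. The power figures rest on the plan's 66% and 33% applying to lasered patients, and on assumed non-lasered shares of 5% and 10%, equal in both arms and with a common outcome.

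The criterion "Uric acid component >50% on stone analysis" raises a query only: is that analysis available before randomisation? The documents do not say, so it is not counted as part of the conflict.

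**What to change.** - **Section 5.2:** state that findings during the operation (direct extraction, failed access, or a tumour first seen at ureteroscopy) do not remove a patient who has been randomised.
- **Section 9.2:** define the primary stone-free analysis as every randomised patient in the assigned arm. Say openly that this replaces enrolled, which under 7.2 means consented.
- **Outcome rule:** take stone-free status from the 2-month CT. Prespecify one analysis rule, the same in both arms and for lasered and non-lasered patients, for those re-treated before the CT or without one. For example, a patient re-treated before the CT, or whose stone was not reached and who has no CT, counts as not stone-free. Any other missing CT follows the missing-data rule for the whole trial, which also needs to be written.
- **Reporting:** give the number of these events by arm.
- **Lasered-only set:** use it as a sensitivity analysis and for the laser efficiency metrics. Fragmentation speed divides by lasing time and cannot be computed without lasing; energy utilisation and lasing activity would be zero or undefined.

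The cost is a wording change, plus dilution of about 2 to 5 points of power compared with excluding the same patients. In small arms each rescored patient counts, so the rule should be fixed before any outcome is seen by arm.

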### 5.3 STRATEGIES FOR RECRUITMENT AND RETENTION

Patients will be recruited from [name] practice. [name] is a world-renown endourologist specializing in the treatment of kidney stone disease. The other members of the research team are currently working under the auspices of [name] and are Mount Sinai clinical and research employees. The clinical staff is involved in this research study have direct access to [name] patient population and are involved in developing patients' treatment plans and managing patient care on a regular basis. The research staff is well trained to design and carry out the administrative and research aspects of this study. They are primarily responsible for educating and consenting patients for the study, and collecting and analyzing data, while ensuring that human research subjects are protected throughout their participation in this study.

## 6 STUDY INTERVENTION(S) OR EXPERIMENTAL MANIPULATION(S)

## 6.1 STUDY INTERVENTION(S) OR EXPERIMENTAL MANIPULATION(S) ADMINISTRATION

#### 6.1.1 STUDY INTERVENTION OR EXPERIMENTAL MANIPULATION DESCRIPTION

For subjects receiving URS, randomization will occur preoperatively. These subjects will be randomized to undergo lithotripsy with either Ho:YAG or TFL lasers.

All subjects will undergo surgical interventions that abide by broadly accepted guidelines and standards of care, allowing for slight variations in technique as seen necessary by the attending surgeon [name].

The type of laser that is chosen in SOC is based on hospital availability. That is, most hospitals only have one laser type to choose from (and that laser type is generally contingent on the biomedical contracts the

hospital holds with the various laser manufacturers). We are uniquely situated at Mount Sinai West in that we have multiple laser systems to choose from. Multiple surgeons share the lasers, and typically [name] will use whichever laser is already in the room or readily available. Approximately 50% of ureteroscopies were performed with each laser, +/- 10%.

# 6.2 FIDELITY

## 6.2.1 INTERVENTIONIST TRAINING AND TRACKING

[name], professor of urology at Mount Sinai West Hospital will be performing the procedures. [name] is a world-renowned expert in these operative techniques.

## 6.3 MEASURES TO MINIMIZE BIAS: RANDOMIZATION AND BLINDING

Patients will be randomized to receive either Thulium or Holmium laser lithotripsy. Patients will be blinded as they will be anesthetized during the operation. Blinding of the operators would not be possible owing to the differences in laser modalities.

We will utilize random.org which is a validated tool that utilizes atmospheric noise to generate random numbers. Each enrolled patient will be given a subject ID and these study IDs will be entered as string of integers to random.org and randomized prior to the initiation of the study. This process will determine group assignments. This will ensure both true randomization and equal allocation.

7 STUDY INTERVENTION/EXPERIMENTAL MANIPULATION DISCONTINUATION AND PARTICIPANT DISCONTINUATION/WITHDRAWAL

#### 7.1 DISCONTINUATION OF STUDY INTERVENTION/EXPERIMENTAL MANIPULATION

No discontinuation will take place as the surgical procedures being performed are part of subjects' standard clinical care.

#### 7.2 PARTICIPANT DISCONTINUATION/WITHDRAWAL FROM THE STUDY

Patients will be considered enrolled in the study once consent has been signed. Participants may discontinue or withdraw from the study for any reason and at any point in time through the conclusion of the study. If a participant desires withdrawal after some or all of their urine samples have been collected or analyzed, their urine samples will be discarded in a biohazard-safe and anonymous fashion.

#### 7.3 LOST TO FOLLOW-UP

All study visits are performed according to the standard of care, and very little failure to follow up is expected.

#### 8 STUDY ASSESSMENTS AND PROCEDURES

### 8.1 ADVERSE EVENTS AND SERIOUS ADVERSE EVENTS

#### 8.1.1 DEFINITION OF ADVERSE EVENTS

Any untoward medical occurrence, unintended sign, symptom, illness or disease temporally associated with the study protocol regardless of the suspected cause.

## 8.1.2 DEFINITION OF SERIOUS ADVERSE EVENTS

An Adverse Event that is considered "serious" if it meets at minimum one of the three Seriousness reporting criterions below:

- 1. Led to death,
- 2. Led to a serious injury which:
  - a. Resulted in a life-threatening illness or injury, or
  - b. Resulted in a permanent impairment of a body structure or a body function, or

c. Resulted in medical or surgical intervention to prevent life-threatening illness or injury or permanent impairment to a body structure or a body function

#### 8.1.2.1 RELATIONSHIP TO STUDY INTERVENTION/EXPERIMENTAL MANIPULATION

All AEs will be assessed for relationship to the study protocol based on the following definitions:

**Not Related:** There is no clear evidence that the AE has a relationship to the study protocol and can be attributed to an underlying or concurrent illness/clinical condition or an effect of another device, drug or treatment.

**Related:** There is a clear causal relationship of the AE to the marketed device or procedure beyond reasonable doubt.

#### 8.1.3 TIME PERIOD AND FREQUENCY FOR EVENT ASSESSMENT AND FOLLOW-UP

All enrolled subjects will be monitored for adverse events by review of the medical record on a monthly basis by [name]. Subjects will have routine follow up scheduled postoperatively at which time in-person visit will be performed and assessment of adverse events may be performed.

# 8.1.4 ADVERSE EVENT REPORTING

Adverse events must be reported to the IRB as soon as possible and no later than **2 working days** after the PI first becomes aware of the event. The PI or designee must record all AE information that can be gathered within the reporting timeframe and enter it onto the AE eCRF. Relevant follow-up information should be submitted to the IRB as soon as it becomes available and/or upon request.

## 8.1.5 SERIOUS ADVERSE EVENT REPORTING

See section 7.1.4

## 8.1.6 REPORTING EVENTS TO PARTICIPANTS

All SAE's or AE's will be reported to affected participants by the principal investigator directly.

## 9 STATISTICAL CONSIDERATIONS

## 9.1 SAMPLE SIZE DETERMINATION

A sample size of 82 patients will be accrued locally. We are enrolling 82 patients to allow for any potential exclusions due to failure to follow up. Ulvik et.al found a stone free rate of 66% and 33% respectively for the thulium fiber laser and holmium laser respectively. Our statistical analysis is to evaluate the superiority of the two laser modalities regarding stone free rate. With an allocation ratio of 1:1, 80% power, alpha of 5%, 66% stone free success of the thulium fiber laser, and 33% stone free success of the holmium laser, our sample size is 33 in each study arm for a total of 66 patients. Based on these calculations and factoring in a 20% dropout rate, we seek to enroll 82 total patients.

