# 9.3.2 ANALYSIS OF THE PRIMARY ENDPOINT(S)

Stone free rates for each laser will be analyzed using the Kruskal-Wallis statistical test. Multiple multivariate regression will also be used to control for stone size, operative time, and other potential confounders.

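### Section 9.1 states 80% power from a formula that does not match the primary test; at the plan's own rates and dropout, the named test has about 77–78%

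*Combined protocol and SAP*

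**What the plan says.** Section 9.1 (Sample Size Determination) gives the design inputs: "With an allocation ratio of 1:1, 80% power", a 5% alpha, "66% stone free success of the thulium fiber laser" and "33% stone free success of the holmium laser". It concludes that "our sample size is 33 in each study arm for a total of 66 patients", and adds the dropout allowance: "factoring in a 20% dropout rate, we seek to enroll 82 total patients". The schema in Section 1.2 splits the 82 into 41 per arm. Section 9.1 does not say which formula was used, which test the calculation is for, or whether the 5% is one- or two-sided.

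Section 9.3.2 names the primary test: "Stone free rates for each laser will be analyzed using the Kruskal-Wallis statistical test".

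Three other places bear on the reading:

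- The Synopsis words the alternative hypothesis directionally ("the thulium laser has a superior stone free rate"), while its null hypothesis is one of no difference.
- Section 7.3 expects few losses to follow-up.
- Section 9.2 puts every enrolled subject in the analysis.

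**The concern.** A stated power should describe the test that will be run, on the number of patients expected to have an outcome. Here the sizing formula and the named test use different variances. The formula that yields 33 per arm uses the separate variances of the two arms; the test uses a variance pooled under the null. With rates as far apart as 66% and 33%, the pooled form needs slightly more patients. In addition, 82 enrolled less 20% falls just short of 66.

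What is at stake is a stated design figure. If the trial finds no significant difference, readers will use the stated power to judge how informative that result is, and the figure is a little too favourable. No patient's treatment depends on it.

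**Working it through.** **Inputs.** From Section 9.1: p₁ = 0.66, p₂ = 0.33, difference d = 0.33, 1:1 allocation, alpha 0.05, power 0.80, dropout 20%, 82 enrolled. From Section 1.2: 41 per arm. From Section 9.3.2: Kruskal-Wallis. Assumption: two-sided testing, since Section 9.1 is silent.

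**1. Reproducing the plan's 33 per arm (unpooled variance).**

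n = (1.960 + 0.842)² × [p₁(1−p₁) + p₂(1−p₂)] / d²
= 7.849 × (0.2244 + 0.2211) / 0.1089 = 32.1, rounded up to **33**.

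The power of this formula at 33 per arm is 81.1%. The one-sided version gives 25.3, rounded up to 26, so the two-sided reading is the one that reproduces the plan.

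**2. What the named test is.** With two groups and a binary outcome, the Kruskal-Wallis statistic equals the Pearson chi-square multiplied by (N−1)/N. It is therefore a pooled-variance test.

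**3. Sizing with the matching formula (pooled variance).** The mean rate is 0.495.

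n = [1.960 × √(2 × 0.495 × 0.505) + 0.842 × √0.4455]² / 0.1089
= (1.386 + 0.562)² / 0.1089 = 34.8, rounded up to **35**.

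The approximate power of this form at 33 per arm is 77.8%.

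**4. Dropout step.** 66 / 0.80 = 82.5, and 82 × 0.80 = 65.6, which is 0.4 patient below 66. In the pooled approximation, moving from 33 to 32.8 per arm lowers power from 77.8% to 77.5%, about 0.3 points.

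**5. Exact power.** This sums the binomial probabilities of every outcome pair for which the test rejects at two-sided 5%, with rates 66% and 33%:

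| Evaluable per arm | Kruskal-Wallis | Pearson chi-square |
|---|---|---|
| 32 + 32 | 79.3% | 79.3% |
| 33 + 32 | 76.5% | 76.7% |
| 33 + 33 | 78.3% | 81.3% |
| 34 + 34 | 76.6% | 77.5% |
| 35 + 35 | 78.5% | 78.5% |
| 36 + 36 | 80.2% | 80.4% |
| 41 + 41 | 88.0% | 88.0% |

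**6. Averaging over dropout.** Exact power is jagged at these sizes, so a single row can mislead. If each of the 41 patients per arm independently has a 20% chance of no outcome, the average exact power is 77.4% for Kruskal-Wallis and 77.8% for the Pearson chi-square.

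**7. Sensitivity to the assumed rates.** At 33 + 33, exact Kruskal-Wallis power is 75.7% for 65.5% versus 33.5%, and 80.8% for 66.5% versus 32.5%. Moving each rate by half a percentage point shifts power by about as much as the gap in question.

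**The case against.** The strongest case on the other side is that Section 9.1 contains no error. Its 33 per arm follows exactly from a textbook formula, and 82 is 82.5 rounded down; losing 16 of 82 (19.5%) leaves exactly 66. A reader might infer that the sample size was miscalculated, or that the dropout arithmetic leaves the trial short. The documents support neither: the first is a choice between two accepted formulas, and the second is 0.4 patient.

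A reader might also infer that the true power is a firm 77%. That is too definite, for three reasons:

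- **Discreteness.** The named test has 79.3% at 32 per arm and 76.6% at 34, so no single row should be pressed. The Pearson chi-square reaches 81.3% at exactly 33 + 33. This objection stands against precision but not against the direction. The Kruskal-Wallis figure is below 80% in every row from 32 to 35 per arm, and the dropout-averaged figures for the two tests differ by only 0.4 points.
- **Dropout.** The 77% assumes that the whole 20% is lost. Section 7.3 expects much less, and at 36 per arm (10 of 82 lost, about 12%) power is already 80.2%. This stands, and the restated power should carry the condition. The rule in Section 9.2 that all enrolled subjects are analysed does not remove it, because the plan gives no way to supply a missing CT outcome.
- **Sidedness.** Two-sided is an assumption. With a one-sided 5% test, the dropout-averaged power would be about 86%. The directional alternative in the Synopsis leaves that reading open, but Kruskal-Wallis is ordinarily non-directional and only the two-sided formula returns 33.

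Finally, the rates themselves are uncertain. Section 2.1 reports 86% versus 49% for the closest earlier comparison, made against an older holmium laser, and describes efficacy relative to a contemporary one as largely unknown. That uncertainty is larger than 2 to 3 points. It limits the importance of this correction without making the stated figure right.

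**Conclusion.** The point holds as a minor correction. The formula that yields 33 per arm does not correspond to the primary test in Section 9.3.2. For that test, at 66% versus 33% and two-sided 5%, exact power is about 78% with 33 evaluable per arm. It averages about 77% if the full 20% of 82 patients have no outcome, and is about 88% if all 82 do. The stated 80% is therefore 2 to 3 points too high under the plan's own rates, dropout and test. Nearly all of the gap comes from the variance formula and almost none from the dropout rounding. The conclusion rests on the two-sided reading, on independent 20% loss in each arm, and on taking 66% and 33% as given. It does not show that 82 patients is the wrong number to enrol.

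**What to change.** Keep 82 patients and restate the power in Section 9.1, for example:

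> Assuming stone-free rates of 66% and 33% and a two-sided 5% Kruskal-Wallis test (for a binary outcome, essentially the pooled chi-square), 82 enrolled gives roughly 77–78% power if 20% have no CT outcome (about 65 evaluable), and about 88% if all 82 are evaluable.

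The authors should confirm that the test is two-sided; if it is not, the figures must be recalculated. The cost is one sentence and a slightly less favourable stated power. No patients are added, and neither the test nor the conduct of the trial changes.
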